4.4 Planning of the trial analyses

Only a final analysis is planned.

4.5 Adjustments

Adjustments may be made to this analysis plan in case of amendments to the protocol, or if phenomena not initially foreseen require statistical adaptations. In all cases, these modifications must be made before the database is frozen.

5 Study populations for analysis

5.1 Definition of analysis populations

5.1.1 Intent-to-treat (ITT) population

The intention-to-treat population is defined as all patients included in the study, regardless of eligibility criteria.

5.1.2 Modified intention-to-treat (mITT) population - evaluable patients

The modified intention-to-treat population is defined as all **evaluable** included patients, regardless of their eligibility criteria and treatment received.

A patient is considered evaluable if:

- he had a chemoembolization and
- received at least one cycle of chemotherapy and
- at least one assessment during the 9 months of follow-up was done

A listing of patients excluded from the ITTm population will be provided with the reasons for exclusion.

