- weakly emetogenic
- hematological toxicity

Dose adaptations for guidance only:

Persistent paresthesias between 2 treatments (grade 2)	Reduce oxaliplatin to 65 mg/m ²
Painful paresthesias or with functional discomfort (grade 3)	Stopping oxaliplatin
Dermal toxicity grade > 2	Reduce bolus 5-FU to 300 mg/m ² Reduce continuous 5-FU to 1800 mg/m ² .
Neutropenia < 1000/mm ³ (> grade 2) or thrombocytopenia < 50,000/mm ³ (> grade 2)	Stop bolus 5-FU and reduce oxaliplatin to 65 mg/m ² if thrombocytopenia
Diarrhea, mucositis or other toxicity grade > 2	Reduce oxaliplatin to 65 mg/m ² . Reduce bolus 5-FU to 300 mg/m ² Reduce continuous 5-FU to 1800 mg/m ² .
Grade 3-4 cardiac, cerebellar or allergy toxicity	discontinuation of chemotherapy

Wait for resolution of toxicities in case of grade 3 or 4 before resuming the cycle.

On the day of the resumption of the cycle D1: 1,500 PNN/mm³ and 100,000 platelets/mm³ are needed to resume the cycle.

VI.2 Chemoembolization

The main adverse effects expected with chemoembolization are:

- Unwanted reflux or passage of microbeads into normal arteries adjacent to the targeted lesion or through the lesion to other arteries or arterial beds
- Non-targeted embolization
- Pulmonary embolization
- Capillary bed saturation and tissue damage
- Ischemic stroke or ischemic infarction
- Rupture of a vessel or lesion and hemorrhage
- Neurological deficits including cranial nerve palsy
- Vasospasm
- Repermeabilization
- Foreign body reactions requiring medical intervention
- Infection requiring medical intervention
- Catheter tip clot formation and subsequent mobilization
- Deaths

Expected effects for the embolization procedure (from CNIHM anticancer files November 2008):

- Fever, right upper liver quadrant pain, vomiting
- Transient thrombocytopenia and liver dysfunction
- Increased transaminases (cytolysis)
- Local ischemic and septic manifestations (cholecystitis, hepatic infarction, hepatic abscess, digestive hemorrhage)
- Renal insufficiency

Adaptations for chemoembolization:

- **The chemoembolization procedure will be stopped in case of:**
 - Inability to catheterize the hepatic artery
 - Dissection of the hepatic artery
 - Anaphylactic shock to contrast medium
 - Per-procedural discovery of portal vein occlusion or arteriovenous shunt
 - near-stasis (stop-flow) observed prior to the full dose of irinotecan

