- If the following grade 3 or 4 toxicities occur as a result of chemoembolization, no additional session will be performed (but FOLFOX will be continued).

- Arteritis
- Grade 3 or 4 hepatic impairment
- Local ischemic and septic manifestations (cholecystitis, hepatic infarction, hepatic abscess, digestive hemorrhage) of grade 3 or 4
- Grade 3 or 4 renal insufficiency
- **The interval between chemoembolization sessions may be extended to allow for recovery of liver function.**
- No dose adjustment of irinotecan is planned for chemoembolization sessions.
- In case of hematological toxicity, FOLFOX dose adjustment rules **will be applied and chemoembolization will be continued.**

In case of doubt, do not hesitate to ask for advice from the study's referring radiologist, [name], through the FFCD.

VII. PATIENT MONITORING DURING TREATMENT AND AFTER WITHDRAWAL OF TREATMENT

Monitoring during treatment:

- **Before each cycle of FOLFOX:**
 - Complete clinical examination including: weight, vital signs, WHO, pain assessment (VAS)
 - Biological check-up: CBC/platelets
 - Adverse event evaluations according to NCI CTC version 4.0
- **Before each chemoembolization session**
 - Complete clinical examination including: weight, vital signs, WHO, pain assessment (VAS)
 - Biological workup consisting of measurements of hematological, nephrological and hepatic parameters: CBC/platelets, blood ionogram, creatinine, albumin, transaminases (AST, ALT), alkaline phosphatases (ALP), total and conjugated bilirubin, PT
 - Adverse event evaluations according to NCI CTC version 4.0

CEA and CA 19-9 assays, as well as thoracoabdomino-pelvic CT and liver MRI will be performed at an initial evaluation between D63 and D70 and then every 2 months after the start of treatment.

For patients participating in the associated 'lipid' translational study, please remember to perform the fasting sample and then technician the sample.

After the chemoembolization treatment period:

All patients will receive chemotherapy with FOLFOX every 2 weeks according to the usual regimen until progression or unacceptable toxicity.

VIII. STOP PROCESSING THE STUDY

The processing of the study will be stopped in case of:

- Investigator's decision
- Major toxicity requiring discontinuation of treatment (despite protocol adaptations)
- Serious or unexpected event requiring discontinuation of protocol treatment
- Progression of the disease
- Patient refusal or withdrawal of consent

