The primary endpoint will be the proportion of patients alive without progression (death will be considered as progression) at 9 months after the start of treatment according to RECIST V1.1 criteria, as assessed by the investigator.

Progression-free survival time will be defined as the time interval between the date of inclusion and the date of progression or death (regardless of cause). For patients alive without progression, the time interval between the date of inclusion and the date of last morphological evaluation will be taken.

XII.2.2 Secondary Criteria

The secondary endpoints will be:

- Tolerance to the treatment
- Response rate according to RECIST v1.1 criteria at 9 months (according to the investigator)
- Response rate according to EASL criteria (assessed by centralized review) at 9 months
- Hepatic progression-free survival according to RECIST v1.1 criteria at 9 months
- Overall survival
- Progression-free survival
- The rate of secondary resections
- Changes in tumor marker levels

Liver progression-free survival will be defined as the time interval between the date of inclusion and the date of liver progression as assessed by the investigator's RECIST V1.1 criteria or death (regardless of cause) or the date of the last morphological assessment for patients alive without progression.

Overall survival will be defined as the time interval between the date of inclusion and the date of death regardless of the cause of death or the date of last news for living patients.

Tolerance to treatment will be assessed by:

- duration of treatment, doses received, dose reductions and deferrals
- Toxicities collected at each monthly visit, and described according to NCI-CTC version 4.0 criteria; Grade 3, Grade 4 and Grade 5 toxicities will be reviewed
- the number and description of SAEs

Changes in tumor marker levels (CEA and CA 19-9) will be assessed throughout the study.

XII.3 Calculation of the number of subjects needed

A 1-step Fleming design will be used, with a one-sided α risk of 5% and a power (1- β) of 90%.

The assumptions are:

- H0: A proportion of patients living without progression of 55% during the first 9 months is uninteresting;
- H1: A proportion of patients living without progression of more than 55% during the first 9 months would show the interest of the treatment; a proportion of 75% is hoped for.

Total number: **48 evaluable patients**

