Taking into account a rate of 20% of patients lost to follow-up or not evaluable, **58 patients should be included**.

At the end of recruitment:

During analysis:

- if 32 or fewer patients are alive without progression, then the treatment is considered ineffective
- if 33 or more patients are alive without progression, then the treatment is considered effective

The decision rule will be adjusted based on the actual number of evaluable patients.

XII.4 Statistical analysis plan

Analysis Populations:

Patients included in the study will be described on an intention-to-treat (ITT) basis as well as patients not evaluable for the primary endpoint.

A patient is considered evaluable if he or she has had chemoembolization and received at least one cycle of chemotherapy and for whom we have at least one evaluation during the 9 months of follow-up.

All efficacy analyses will be performed on a modified intention-to-treat basis (evaluable patients) included in the study regardless of eligibility criteria and treatment received.

Tolerability population: the ITT population that received at least one dose of the treatments.

In all cases of discontinuation, the patient remains in the intention-to-treat analysis. There is no exclusion period for a subsequent therapeutic trial.

Key analyses:

A statistical analysis plan will be written prior to freezing the database.

The description of clinical and medical variables will be done using percentages (95% confidence interval) for qualitative variables and mean (standard deviation) and median (Min-Max) as well as inter-quartile range (Q1-Q3) for quantitative analysis.

Survivals and times will be estimated by the Kaplan Meier (KM) method. They will be described by medians and rates at different time points with their 95% confidence intervals.

Median follow-up time will be calculated using the reverse Kaplan Meir method.

The time to onset of grade 3/4/5 toxicity will be estimated using the Kaplan Meier method.

Exploratory Analyses:

- research into factors predictive of progression-free survival and/or overall survival

XII.5 Independent Committee Supervisory Committee

An independent committee composed of 1 clinician / 1 methodologist / 1 pharmacovigilant expert will be formed before the start of the trial.

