7.3.1 Definition of the primary endpoint

The primary endpoint is to evaluate the rate of patients alive without progression at 9 months after the start of treatment. Progression is defined as radiological progression according to RECIST V1.1 criteria, as assessed by the investigator.

Patients who progressed or died (from any cause) within 9 months of initiation of therapy (Day 1 of Cure 1) will be considered to have failed the primary endpoint at 9 months.

The scans selected for analysis will be the scans before and up to 9 months with a +/- 1 month window.

Patients without a 9-month evaluation will be reviewed according to the following rules:

- If the patient has a late assessment (10 months or more) and is not progressing at that time, then they will be considered progression-free at 9 months.
- If the patient has documented progression at more than 9 months without imaging at 9 months, then that patient will be considered to be in progression at 9 months. If progression is documented at more than 11 months, the patient will not be considered to be in progression at 9 months.
- If progression is documented before the 9-month assessment, the patient is considered to be in progression at 9 months.

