7.3.2 Evaluation of the primary endpoint

The primary endpoint will be assessed on the ITTm population. This criterion will be described according to the usual descriptive statistics. A one-sided 95% confidence interval will be calculated using the exact method.

The decision rules to be applied on 48 patients evaluable in the analysis (ITTm population) are:

- If 32 or fewer patients are alive without progression, then the treatment is considered ineffective.
- If 33 or more patients are alive without progression, then the treatment is considered effective.

These may be adjusted based on the actual number of evaluable patients included.

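### The 33/48 decision rule is applied to a set defined by events after treatment starts, so some early failures, and some never-embolized successes, leave the denominator

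*SAP*

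**What the plan says.** **Endpoint.** Protocol XII.2.1 defines the primary endpoint as the "proportion of patients alive without progression (death will be considered as progression) at 9 months" after the start of treatment. SAP 7.3.1 counts as failures "Patients who progressed or died (from any cause) within 9 months of initiation of therapy", with Day 1 of cycle 1 as the origin. It adds: "Progression is defined as radiological progression according to RECIST V1.1 criteria, as assessed by the investigator".

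**Decision set.** SAP 7.3.2 states: "The primary endpoint will be assessed on the ITTm population". The 33/48 rule is attached to that set and to no other. Protocol XII.4 calls a patient "evaluable if he or she has had chemoembolization and received at least one cycle of chemotherapy" and has at least one evaluation during the 9 months. SAP 5.1.2 sets the same three conditions, the third being that "at least one assessment during the 9 months of follow-up was done". Neither document makes an exception for death, and neither says whether an assessment means tumour imaging. Both also describe the set as independent of the treatment received, although they require two treatments.

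**Timing.** The first DEBIRI is planned at D17 (Protocol synopsis and V.3). CT and liver MRI "will be performed at an initial evaluation between D63 and D70" (Protocol VII).

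**Other reporting.** The SAP section 7 table also plans the 9-month rate in the ITT and per-protocol sets. SAP 7.4.6 gives an ITT Kaplan-Meier rate at 9 months. SAP 5.1.2 promises a listing of exclusions with reasons, and Protocol XII.4 a description of the non-evaluable patients.

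**The concern.** Whether a patient counts depends on two things that happen after treatment starts and are linked to outcome: reaching a DEBIRI session and reaching an assessment. With no control arm to share the selection, it acts directly on the comparison with 55%.

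Three kinds of patient are affected:

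- those who start FOLFOX and die before the first DEBIRI, or after it but before any assessment. They are failures by definition but are not counted;
- those with documented RECIST progression before the first DEBIRI. This needs an unscheduled scan, so it should be uncommon;
- those who never receive DEBIRI for a reason that is not an endpoint failure. Examples are "Inability to catheterize the hepatic artery" (Protocol VI.2) or a missed pre-procedure laboratory limit (V.2.6). Some of them may be progression-free at 9 months, and these successes are lost.

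The first two push the observed rate up and the third pushes it down. The 20% allowance restores the sample size, but it pools neutral losses with endpoint failures and corrects neither distortion.

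**Working it through.** **Inputs.** From SAP 4.3: null rate 0.55, hoped-for rate 0.75, one-sided α 5%, power 90%, 48 evaluable patients, 58 included, success at 33 or more. The documents do not give the number of excluded failures or of excluded progression-free patients. I assume small values and show the range.

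**1. The plan's own figures.** Fleming's approximation gives n = [(1.645·√(0.55·0.45) + 1.282·√(0.75·0.25)) / 0.20]² = 47.14, so 48. The cut-off is 48·0.55 + 1.645·√(48·0.55·0.45) = 32.07, so 33. Inclusion is 48·1.2 = 57.6, so 58. The stated design reproduces. Exact binomial values for 33/48 are α = 3.7% and power = 87.7%.

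**2. Effect on the error rate.** Let d be the excluded early failures and s the excluded never-embolized progression-free patients. Other exclusions are neutral, and the true rate is 0.55 in all 48 + d + s. The success rate among the 48 analysed is then

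p = [0.55·(48 + d + s) − s] / 48,

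and the error is P(X ≥ 33 | 48, p). For d = 1, s = 0, p = 0.55·49/48 = 0.5615.

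| d | s | p | error of 33/48 |
|---|---|---|---|
| 0 | 0 | 0.550 | 3.7% |
| 1 | 0 | 0.561 | 5.2% |
| 2 | 0 | 0.573 | 7.1% |
| 3 | 0 | 0.584 | 9.5% |
| 1 | 1 | 0.552 | 3.9% |
| 2 | 1 | 0.564 | 5.5% |
| 2 | 2 | 0.554 | 4.2% |
| 0 | 2 | 0.531 | 2.0% |

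p exceeds 0.55 only when 0.55·d > 0.45·s, that is, when failures are more than 45% of these d + s exclusions.

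**3. Effect on a given result** (exact one-sided 95% lower limits):

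- 33/48: 56.0%, effective. Restore one failure, 33/49: 54.7%. The exact cut-off at 49 is 34, so not effective.
- 34/48 survives two restored failures (34/50: 55.5%) but not three (34/51: 54.3%).
- 32/48: 53.9%, not effective. Restore two progression-free patients, 34/50: 55.5%, effective.

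**4. Exact rules for a larger set** (largest attainable α not above 5%):

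| n | cut-off | α at 55% | power at 75% |
|---|---|---|---|
| 48 | 33 | 3.7% | 87.7% |
| 49 | 34 | 2.9% | 85.8% |
| 50 | 34 | 4.3% | 90.2% |
| 51 | 35 | 3.3% | 88.5% |
| 52 | 35 | 4.9% | 92.2% |
| 53 | 36 | 3.8% | 90.8% |
| 54 | 37 | 3.0% | 89.3% |
| 55 | 37 | 4.4% | 92.7% |
| 56 | 38 | 3.5% | 91.5% |
| 57 | 38 | 5.0% (0.0495) | 94.2% |
| 58 | 39 | 3.9% | 93.2% |

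**5. Power if 75% holds only in the 48 now called evaluable.** Added failures raise the cut-off but bring no successes, so power is P(X ≥ r | 48, 0.75): 87.7% at r = 33, 80.0% at r = 34 (1 or 2 added) and 69.9% at r = 35 (3 or 4 added).

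**The case against.** The strongest reply is that this is a deliberate evaluable-patient design, sized with a 20% allowance, and that the affected group is small. Entry requires WHO status of 2 or less, life expectancy of at least 3 months and almost no extra-hepatic disease. Early deaths should therefore be few, and documented progression before D17 rarer still. If the clinical examination before each FOLFOX cycle counts as an assessment, most deaths before first imaging would stay in the set. The ITT rate, the ITT Kaplan-Meier estimate and the exclusion listing would let a reader see the loss. The flip from 33/48 to 33/49 needs a result exactly on the cut-off and partly reflects discreteness, since 34/49 has α of only 2.9%.

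Most of this stands as a limit on size, and it does not remove the point. On the broad reading of assessment, the DEBIRI condition still drops every failure before the first session. The ITT outputs disclose the problem but do not drive the verdict. Sizing for non-evaluable patients does not make outcome-linked exclusion neutral.

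A reader might go further and infer that the rule always favours the treatment, or that most of the 10 patients between 48 and 58 are hidden failures. The documents support neither. They name several reasons for missing DEBIRI that are not failures, and they give no count of early failures.

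**Conclusion.** The concern holds in a limited form. The decision set depends on post-start events, and the documents contradict themselves: SAP 7.3.1 and Protocol XII.2.1 call an early death a failure, while SAP 5.1.2 and Protocol XII.4 can remove it before the rule is applied. The direction of bias is not established, and the size is probably modest. One excluded failure takes the error to about the nominal 5% limit; two or three exceed it if nothing offsets them. An equal number of excluded progression-free patients brings it back below 5% in the cases shown.

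These figures assume a true rate of 55%, 48 analysed and all other exclusions neutral. The textual gap is certain; the number and mix of affected patients is not. It should be fixed because the only formal verdict of the trial can turn on one patient and the repair is simple.

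**What to change.** In SAP 5.1.2 and 7.3.2 and Protocol XII.4:

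- Apply the decision rule to all included patients who started cycle 1 of FOLFOX, whether or not DEBIRI was given or imaging done. This matches the SAP 7.3.1 origin.
- Classify them by the existing SAP 7.3.1 rules: death or documented progression within 9 months is a failure, progression-free at 9 months a success.
- Count patients who are alive with no tumour imaging as failures in the decision analysis, with a sensitivity analysis that leaves them out. If they were dropped while un-imaged deaths were kept, membership would again depend on outcome.
- State that assessment means tumour imaging.
- Replace the 33/48 rule by the exact cut-off for the actual n, as tabulated above from 33/48 to 39/58.
- Report the current modified ITT result as supportive, and remove the wording that calls the set independent of treatment received.
- State in SAP 4.3 which set the 75% refers to.

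**Cost.** The 9-month rate is already planned for ITT, so no new data are needed. It does change the primary analysis population, so the protocol text must be amended and, under SAP 4.5, the SAP change made before database freeze. The reported rate may be less favourable, and FOLFOX-only patients can count as successes, which is why the present set should stay as a supportive analysis. Power at 39/58 is 93.2% if 75% holds in all who start treatment. If it holds only in the 48 now evaluable, power falls from 87.7% to 80.0% with 1 or 2 added failures and to 69.9% with 3 or 4.

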5.1.3 Tolerance population (TP)

The tolerance population is defined as all patients included in the study who received at least one dose of FOLFOX treatments.

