Study design and treatment plan	
Microbeads (100-300μm), loaded with irinotecan (DEBIRI). The maximum dose per procedure is 100 mg of irinotecan, combined with intravenous FOLFOX.
 
For patients with unilobar or bilobar liver involvement, DEBIRI will be injected at D17 and D45 (after the 2nd and 4th cycle of systemic chemotherapy with FOLFOX).
 
Patients with bilobar involvement but for whom the investigator decides that the treatment will be unilobar and sequential, there will be 4 sessions. Thus, the right and left livers will be treated alternately. The DEBIRI administrations will then be performed at D17, D31, D45, D59, or in case of a shift in chemotherapy treatment, after the 2^{ème}, 3^{ème}, 4^{ème} and 5^{ème} cycle of FOLFOX.
 
FOLFOX will be administered every 2 weeks until progression or unacceptable toxicity.

Statistical methods	
A 1-step Fleming design will be used, with a one-sided α risk of 5% and a power (1-β) of 90%.
 
The assumptions are:
 
 • H0: A proportion of patients living without progression of 55% during the first 9 months is uninteresting; • H1: A proportion of patients living without progression of more than 55% during the first 9 months would show the interest of the treatment; a proportion of 75% is hoped for.

	
Total number: 48 evaluable patients
 
Taking into account a 20% rate of lost to follow-up or non-evaluable patients, 58 patients should be included.
 
At the end of recruitment:
 
During analysis:
 
 - if 32 or fewer patients are alive without progression, then the treatment is considered ineffective - if 33 or more patients are alive without progression, then the treatment is considered effective 
The decision rule will be adjusted based on the actual number of evaluable patients.

Number of subjects needed	58
Associated translational studies	
 - On lipid parameters: The objective of this study will be to evaluate the impact of the different parameters of the lipid profile and the metabolism of lipoproteins on the response to treatment. - On Pathology: At the end of the study, if a sufficient number of patients have undergone secondary resections of liver metastases, a collection of surgical parts will be organized. An anatomopathological study of the tumor parenchyma and the healthy parenchyma resected after DEBIRI treatment will be performed.

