Intravenous triple therapy combining 5FU, oxaliplatin, and irinotecan has been evaluated in randomized trials (Falcone et al, (2); Souglakos et al, (3)). They showed good response rates (43-60% according to RECIST criteria), progression-free survival (about 62% at 9 months), secondary resection rates of liver metastases and overall survival. Tolerability was acceptable if the WHO performance status at inclusion was <2, bilirubinemia <1.5 times LNS, and primary neutropenia prophylaxis (G-CSF) was administered. These trials suggest that the combined use of 5FU, oxaliplatin, and irinotecan is an option in the treatment of first-line metastatic colorectal cancer.

Intra-arterial chemotherapy

It has been shown in numerous trials over the past 20 years that intra-arterial chemotherapy can improve response rates and overall survival, particularly in patients with liver-limited metastatic disease. In patients with liver-limited metastases, locoregional chemotherapy exposes liver tumor cells to high concentrations with minimal systemic toxicity. However, FUDR and, more recently, oxaliplatin have been the most extensively tested drugs by this route, with high response and secondary resection rates of liver metastases (4-7), but no large phase III is currently available to validate their use in daily practice. In addition, there is a clear lack of standardization of the therapeutic protocol for IA injection and the use of intra-arterial devices is still limited to very specialized centers.

Advantages of the DEBIRI

An intra-arterial hepatic chemotherapy protocol with irinotecan-loaded microbeads (DEBIRI) has recently been developed. Preliminary results are promising. A phase II study of 82 patients with unresectable liver metastases, after failure of two lines of chemotherapy, treated with DEBIRI achieved a 78% response rate and improved quality of life in 90% of patients (8). Acute toxicity is common (post-embolism syndrome in 80% of cases) but easily manageable.

This treatment was also tested in another second- or higher-line study in 55 patients with colorectal cancer with unresectable liver metastases (9). Results showed a 75% response rate at 1 year and a median overall survival of 19 months. This treatment also appeared to be well tolerated, with 28% grade 1-3 toxicities. It did not appear to be more toxic in combination with systemic chemotherapy (continuous IV or oral 5FU, n = 16) than alone.

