7.5.1 Chemoembolization

Chemoembolization therapy (CHE) will be described by:

- The number of HEC performed per patient and the total number of HEC performed by type of treatment. Causes will be described for patients who did not have the total number of HECs as per the protocol.
- The number and percentage of patients who had 1 HEC, 2 HEC, 3 HEC or 4 HEC according to the type of treatment (uni-lobar or bi-lobar)

- The type of treatment, the lobe involved, the dose of irinotecan administered. Causes will be described when the dose of irinotecan was not administered completely.
- The number of HEC deferrals and the causes of deferrals
- The number and percentage of patients treated with G-CSF

The consequences of treatment will also be described:

- The length of hospitalization
- The number and percentage of patients who experienced side effects during the procedure. A listing of other side effects during the procedure will be reported.
- Number and percentage of patients with pain >3 (VAS)
- The pain assessment (VAS) before HEC and within 24 hours after HEC will be described by grade (frequency of VAS for all HEC).

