7.5.3 Toxici

Toxicities during treatment will be described according to NCI-CTC version 4.0 criteria by:

- The number of patients and toxicities by maximum grade and type;
- The number and percentage of patients with at least one toxicity across all courses by grade;
- The number and percentage of patients with at least one maximum grade 3-4-5 toxicity over all courses or at least one maximum grade 1-2 toxicity;

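### The SAP omits the protocol's time-to-onset analysis of grade 3/4/5 toxicity and sets no chemoembolization-exposed denominator for procedural side effects

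*SAP*

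**What the plan says.** Protocol XII.4, under its key analyses, states: "The time to onset of grade 3/4/5 toxicity will be estimated using the Kaplan Meier method". The same section sets the safety population: "Tolerability population: the ITT population that received at least one dose of the treatments".

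SAP 5.1.3 narrows this to FOLFOX: "The tolerance population is defined as all patients included in the study who received at least one dose of FOLFOX treatments". The population table in SAP section 7 marks the two tolerance rows, treatment administration and toxicities, for this set and no other. The population line under SAP 7.5 is blank.

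SAP 7.5.1 asks for "The number and percentage of patients who experienced side effects during the procedure" and for the number and percentage with pain above 3 on the VAS, and names no denominator for either. SAP 7.5.3 asks for "The number and percentage of patients with at least one toxicity across all courses by grade", together with counts by maximum grade and type and a grade 3-5 summary, also over all courses.

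On timing, the protocol synopsis says "DEBIRI will be injected at D17 and D45 (after the 2nd and 4th cycle of systemic chemotherapy with FOLFOX" for the 2-session scheme and "The DEBIRI administrations will then be performed at D17, D31, D45, D59" for the 4-session scheme. FOLFOX then continues every two weeks until progression or unacceptable toxicity.

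**The concern.** Protocol XIII gives feasibility, safety and efficacy of FOLFOX plus DEBIRI as the aim, and tolerance is the first secondary endpoint. There is no control arm, so when an event occurs relative to the chemoembolization sessions is one of the few internal clues a reader has. The plan weakens this in two ways.

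First, the one analysis the protocol planned for the timing of severe toxicity in general is missing from the SAP, and what remains is a worst grade over the whole treatment.

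Second, exposure to DEBIRI does not follow from exposure to FOLFOX. A patient enters the tolerance set at the first FOLFOX dose, but the first session comes about 17 days later and depends on the liver, blood and portal checks of Protocol V.2.6. Some patients may stop or be held back before then. The SAP foresees this, because its evaluability rule in 5.1.2 requires a chemoembolization. A percentage of patients with side effects during a procedure should not count patients who had none.

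**Working it through.** **1. Tracing the time-to-onset analysis.** The planned estimate in Protocol XII.4 was looked for in each place where the SAP could carry it.

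- SAP 6.5: Kaplan-Meier is described for survival data and, in reverse form, for follow-up. Toxicity is not mentioned.
- SAP section 7 table: the tolerance block has rows for administration and toxicities only.
- SAP 7.5 to 7.5.4: duration, doses, deferrals, worst grade, and an SAE summary supplied by pharmacovigilance. There is no time to onset.

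No reason for the omission is given.

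**2. What the all-course summary hides.** SAP 6.2 sets 1 month = 30.4375 days, so 9 months = 9 × 30.4375 = 273.9 days, or 273.9/14 = 19.6 two-week cycles. The last session is at D45 or D59: 45/273.9 = 16% and 59/273.9 = 22% of that span. A patient still on FOLFOX at 9 months has spent roughly four-fifths of the time after the last session. Some toxicities are expected from both components. Vomiting and transient thrombocytopenia are listed for the embolization procedure in Protocol VI.2. Emetogenic effects and thrombocytopenia also appear under FOLFOX in VI.1. For these, a worst grade over all courses does not show in which period the event fell.

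**3. Denominator: the plan's own counts first.** The design in SAP 4.3 (55% versus 75%, one-sided 5%, power 90%) gives, by normal approximation, n = ((1.645·√(0.55·0.45) + 1.282·√(0.75·0.25))/0.20)² = 47.1, rounded up to 48. Inflation is 48 × 1.20 = 57.6, rounded to 58. Both stated figures reproduce. The planned gap is 58 − 48 = 10 patients. (Read literally, 20% of 58 would be 11.6; the gap between the stated counts is used here.)

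**4. Size of any dilution.** Let k be the number of FOLFOX-treated patients who never had a chemoembolization. With e patients affected among 58 − k exposed, the rate in exposed patients is p = e/(58 − k). On the FOLFOX-based set it is reported as e/58 = p × (58 − k)/58. The documents do not give k, so this is a range under assumption:

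| k | factor | 10% shown as | 30% shown as | 50% shown as |
|---|---|---|---|---|
| 0 | 1.000 | 10.0% | 30.0% | 50.0% |
| 3 | 0.948 | 9.5% | 28.4% | 47.4% |
| 5 | 0.914 | 9.1% | 27.4% | 45.7% |
| 10 | 0.828 | 8.3% | 24.8% | 41.4% |

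The last row is an upper bound on the planned counts. It needs all 10 patients in the gap to have had FOLFOX and no DEBIRI. Any of them who never started FOLFOX leave the tolerance set, and any who had DEBIRI but no tumour assessment are exposed.

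As an illustration at that bound, 14 affected patients are 14/48 = 29.2% (exact 95% CI about 17 to 44%) or 14/58 = 24.1% (about 14 to 37%).

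**The case against.** The strongest reply is that SAP 7.5.1 never says its percentages use the tolerance set. It counts patients with one to four sessions and has no zero category, takes VAS frequencies over all sessions, and speaks of effects during the procedure. All of this suggests a treated denominator, and a sensible programmer might use one. The table row on administration does not name side effects or pain. This stands in part: the defect is an unstated denominator whose only written default is the FOLFOX set, not a rate known to be wrong. A reader could also partly undo any dilution from the session counts and the listing of patients excluded from the modified ITT set.

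It is also fair that timing is not wholly lost. SAP 7.5.1 covers effects during the procedure, pain within 24 hours, hospital stay and deferrals, and Protocol XII.5 plans an SAE analysis after the first 10 patients treated intra-arterially. None of these shows when general toxicities occur.

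For a combination regimen, a set based on any dose, with maximum grade, is a reasonable overall summary. The protocol's own definition would give almost the same patients, since FOLFOX comes first. So SAP 5.1.3 is not wrong in itself; an exposed subset is missing beside it.

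Three stronger readings are tempting, and the documents do not support them:

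- *Late neuropathy cannot be separated from DEBIRI toxicity.* SAP 7.5.3 tabulates by type, and neuropathy is listed as an oxaliplatin effect.
- *The G-CSF percentage is diluted too.* Protocol V.3 lists G-CSF among the FOLFOX preventive treatments as well, so a FOLFOX denominator is reasonable.
- *Rates will be 7 to 14 points too low.* This takes the protocol's "post-embolism syndrome in 80% of cases" and computes 0.80 × 53/58 = 73% or 0.80 × 48/58 = 66%. The 80% comes from patients who had failed two lines of chemotherapy, the 53 is invented, and the syndrome is not a named item in SAP 7.5.1.

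**Conclusion.** The point holds in two parts. The firmer one needs no assumption: a key safety analysis in Protocol XII.4 is absent from the SAP without explanation, and the all-course worst grade in 7.5.3 does not replace it for toxicities that both components can cause.

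The second is conditional. If the SAP table is followed as written, percentages for procedural side effects and pain >3 include FOLFOX-treated patients with no chemoembolization. The factor is (58 − k)/58, from 1 at k = 0 to 0.83, a relative understatement of 17%, at k = 10. It rests on 58 inclusions, on the tolerance set being the denominator, and on a k that the documents do not give. The true effect may be nil.

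A reader might go further and infer that no conclusion on tolerance can be drawn. That does not follow: overall toxicity of the combination is still described by type and grade, and 7.5.1 reports on the procedures separately. The primary efficacy test is not affected.

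**What to change.** - **SAP 7.5.3:** restore the Kaplan-Meier analysis of time to first grade 3/4/5 toxicity. State its time origin and censoring date, which XII.4 leaves open; the 30-day toxicity follow-up in Protocol VIII offers a natural limit.
- **SAP 5.1:** add a set of all patients with at least one chemoembolization attempted, including procedures stopped during catheterization.
- **SAP 7.5.1:** use that set as the denominator for procedural side effects and pain, and add per-session rates.
- **SAP 7.5.3:** show grade 3-5 toxicity for the DEBIRI phase (first session to 30 days after the last) and for the time afterwards. Label this descriptive, because FOLFOX runs through both periods and a phase split cannot attribute cause.
- **SAP 7.5:** fill in the population line. Keep the FOLFOX-based set for overall toxicity and G-CSF use.

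The cost is SAP wording and a few extra tables, and SAP 4.5 allows such changes before the database freeze. Procedure-related rates may come out slightly higher. No new data should be needed if toxicities are recorded before each cycle and session, as Protocol VII provides. XII.2.2 speaks of monthly visits, and the CRF is not among the documents, so check that onset can be dated finely enough.
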